14. ANALYSIS SOFTWARE

Statistical analyses will be performed using Version 9.4 (or newer) of SAS[®] on a suitably qualified environment.

15. CHANGES TO ANALYSIS SPECIFIED IN PROTOCOL

The following changes were made to the analyses specified in the protocol:

- The mITT set, which includes subjects with a baseline and at least one post-baseline GA lesion assessment, replaced the ITT set as the main efficacy population to be aligned with the primary analysis methodology.
- The change in GA lesion(s) size at Month 24 between PM and Sham was to be the third hypothesis tested in the hypotheses testing strategy as specified in the protocol. This was removed from the hypotheses testing strategy in the SAP.
- The hypotheses testing strategy and α allocation for the key secondary endpoints was not precisely specified within the protocol and has been clarified to follow the hypotheses testing procedure and α allocation as described in Section 6.3.1.
- Several new exploratory endpoints not specified in the protocol were added.
 - NEI-VFQ-39 distance activity, composite, near activity subscale score
 - NEI-VFQ-25 driving subscale score
 - Progression from iRORA to cRORA
 - Progression from large drusen to iRORA or cRORA
 - Change in the distance of the atrophy junction to the fovea and without subfoveal atrophy to subfoveal atrophy conversion
- No pre-specified analysis will be performed on the secondary endpoint of change from baseline in LLD over time. This data will only be listed.
- No formal interim analyses are planned for this study: however, analyses of interim data from Months 12 to 24 that may support regulatory submissions may be conducted.
- The pharmacokinetic endpoints of AUC, C_{\max} , and T_{\max} were specified in the protocol; however, since only trough concentrations were collected throughout the study it is only possible to assess C_{\max} . C_{\max} should occur at Day 7 following pegcetacoplan treatment. Therefore, the concentration on Day 7 will be used ($C_{\text{Day 7}}$) as the observed C_{\max} values.
- Other minor editorial changes were made to provide clarity.

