## 12.7. Efficacy Analyses

The primary, secondary, and exploratory efficacy analyses will be performed using the ITT set and presented by treatment group.

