**Step 1.** The mean GA lesion growth at 12 months will be compared between the PM group and the Control at the  $\alpha$  level of 0.0495. If the null hypotheses of no difference between groups in this step is rejected, the testing proceeds to **Step 2** and **Step 3**. If it's not rejected, the testing procedure stops at this step.

**Step 2.** The mean GA lesion growth at 12 months will be compared between the PEOM group and the Control at the  $\alpha_1$  level. If the null hypotheses of no difference between groups in this step is rejected, the  $\alpha_1$  level will be passed down to **Step 3**. The actual value of  $\alpha_1$  will be specified in the SAP and it will be defined to ensure an adequate power of at least 80% for the comparison in this step.

**Step 3.** The mean GA lesion growth at 24 months will be compared between the PM group and the Control at the  $\alpha$  level of **0.0495** if the null hypotheses are rejected at both **Step 1** and **Step 2**; or at the  $\alpha$  level of **(0.0495 –  $\alpha$ 1)** if **Step 2** testing does not reject the null hypothesis. If the null hypothesis at this step is rejected, the  $\alpha$  level used at this step will be passed down to the next step of testing. If it's not rejected, the testing procedure stops at this step.

**Step 4.** The prioritization and alpha allocation for the remaining secondary endpoints will be specified in the SAP.

The following sensitivity and supportive analyses will be performed to evaluate the robustness of the results from the primary analysis method:

- Analyses will be repeated using the modified ITT and PP sets
- Primary and secondary endpoints will also be summarized with no pooling of the 2 sham arms. The comparison for pegcetacoplan and sham injection within each dose regimen (ie, PM vs SM and PEOM vs SEOM) will be conducted
- Multiple imputation methods and other sensitivity analyses will be explored, and details will be provided in the SAP

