4.3. Modified Intent-to-Treat Set

The modified ITT (mITT) set consists of all randomized subjects who receive at least one injection of pegcetacoplan or sham and have baseline and at least one post-baseline value of GA lesion area in the study eye as assessed by FAF. Subjects will be analyzed in the treatment arm assigned at randomization.

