6. EFFICACY ANALYSES

Efficacy analysis including primary, key secondary, secondary, and exploratory analysis will be performed primarily using the mITT set, with subjects grouped according to the treatment assigned at randomization. Available data from all randomized subjects regardless of adherence to the protocol will be included in the efficacy analyses; this includes data from subjects who discontinued study drug early but continued with study assessments. All efficacy data will be listed for the ITT set.

Unless otherwise noted, hypothesis testing and estimation of treatment effects will be performed with a mixed effect model for repeated measure (MMRM) that includes data from all three treatment arms (PM, PEOM, and Sham). The Sham arm will represent the pool of the two sham treatment groups: SM and SEOM (i.e., the two sham arms will be pooled into a single “control” group). All hypothesis tests for efficacy endpoints will be two-sided.

Unless otherwise noted, analysis of efficacy endpoints (primary, key secondary, secondary, and exploratory) in the overall population will be adjusted for the following randomization stratification factors (actual status) and baseline covariates:

For primary efficacy endpoint

- Presence of CNV in the fellow eye (yes; no)
- Baseline GA lesion area ($< 7.5 \text{ mm}^2$ or $\geq 7.5 \text{ mm}^2$)

For key secondary, secondary, and exploratory endpoints

- Presence of CNV in the fellow eye (yes; no)
- Baseline GA lesion area ($< 7.5 \text{ mm}^2$ or $\geq 7.5 \text{ mm}^2$)
- Baseline value of the endpoint

Of note, the randomization stratification factors were assessed at the screening visit. In the event of a change in status in the GA lesion area between the screening visit and the baseline visit (i.e., GA lesion area $< 7.5 \text{ mm}^2$ at screening to $\geq 7.5 \text{ mm}^2$) then the baseline status will be used.

If a statistical model is not directly specified and if necessary, data will be analyzed with the following approaches:

- For continuous endpoints, the MMRM analysis described for the primary endpoint in Section 6.2.2.
- For categorical or ordinal variables, a Cochran Mantel Haenszel (CMH) test with the baseline category status, presence of CNV in the fellow eye (yes or no), and baseline GA lesion area ($< 7.5 \text{ mm}^2$ or $\geq 7.5 \text{ mm}^2$) as stratification factors.

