6.1. Estimands

The primary scientific research question of this study is to assess the effect of pegcetacoplan compared with that of sham at Month 12 regarding the impact on GA lesion progression under-real-life conditions following the ITT principal.

The primary estimand in the study is defined through the following 5 attributes:

- **Population:** GA subjects defined through inclusion and exclusion criteria in the mITT population.
- **Treatment conditions:** The treatment regimen of interest in this study is PM, PEOM, and Sham.
- **Variable (or endpoint):** Change in total area of GA lesions in the study eye from baseline measured by FAF to Month 12.
- **Strategy for addressing intercurrent events:** See description of intercurrent events below.
- **Population-level summary:** Difference in mean change of GA lesion from baseline to Month 12 between pegcetacoplan and sham groups according to MMRM analysis.

The intercurrent events that will be considered are:

- Treatment discontinuation
- Lost to follow up
- Withdrawal from the study

The intercurrent events will be handled with a treatment policy strategy whereby any measured value will be used as is. Missing data resulting from these intercurrent events will be handled implicitly within the MMRM analysis that assumes missing at random.

The key secondary estimands will be defined and analyzed in the similar fashion as the primary estimand. The primary and key secondary estimands are summarized in [Table 2](#).

Table 2: Estimands of Study

Estimand	Definition	Attributes			
		A: Population	B: Variable (or endpoint)	C: Strategy for addressing intercurrent event	D: Population-level summary
		Main Analyses			
Primary	The effect of pegcetacoplan compared to sham at Month 12 in impact on GA progression	mITT	Change in the total area of GA lesions from baseline measured by FAF to Month 12	
 Treatment policy strategy for subjects who discontinue treatment, are lost to follow-up, or withdraw from the study 	Difference in mean change of GA lesion from baseline at Month 12 between pegcetacoplan and sham groups based on MMRM analysis

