6.3. Analyses of Key Secondary Efficacy Endpoints

The key secondary efficacy endpoints are listed in Section 2.2.2. At the Month 12 reporting, all key secondary efficacy endpoints will be evaluated based on data from baseline to Month 12 (see Section 3.5). For the Month 12 analyses, post-baseline visits, up to and including Month 12, will be included and nominal p-values will be presented. At the time of the final study analysis, all key secondary efficacy endpoints will be evaluated based on data from baseline to Month 24, and formal statistical testing for key secondary endpoints will be performed as described in Section 6.3.1. Unless otherwise specified, all secondary efficacy endpoints will be analyzed for the mITT set.

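### The SAP's mITT set leaves no efficacy analysis on all randomised subjects: minor for the main FAF model, but unjustified for the imputation analyses and NL-BCVA

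*SAP*

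**What the plan says.** Protocol Section 12.7 states: "The primary, secondary, and exploratory efficacy analyses will be performed using the ITT set and presented by treatment group". Section 12.7.1 gives mITT a supporting role: "Analyses will be repeated using the modified ITT and PP sets".

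The SAP states that it supersedes the protocol's analysis plan, and it reverses these roles. Under SAP Section 6, efficacy analysis "will be performed primarily using the mITT set, with subjects grouped according to the treatment assigned at randomization". Section 4.3 admits only randomised subjects who received an injection and who "have baseline and at least one post-baseline value of GA lesion area in the study eye as assessed by FAF". Section 15 discloses the switch, saying that the mITT set "replaced the ITT set as the main efficacy population to be aligned with the primary analysis methodology", but mentions only the FAF conditions, not the injection.

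The mITT set then governs the hypotheses (6.2.1), the estimands (6.1 and Table 2), the sensitivity analyses (6.2.3) and both imputation analyses (6.2.3.1). For the key secondary endpoints, Section 6.3 says that, unless otherwise specified, "all secondary efficacy endpoints will be analyzed for the mITT set". Sections 6.4 and 6.6 do the same for other secondary and exploratory endpoints. The per-protocol sets (4.5) are subsets of mITT. ITT survives in listings and in descriptive tables of disposition, baseline and exposure. The genotyping set is drawn from ITT, but that work goes to a separate report.

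Two statements point the other way. Section 6 says that available data from every randomised subject enter the efficacy analyses. Section 6.1 frames the research question as "the impact on GA lesion progression under-real-life conditions following the ITT principal" and applies a treatment-policy strategy to treatment discontinuation, loss to follow-up and withdrawal.

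**The concern.** Membership of mITT depends on something measured after randomisation. A subject who withdraws or is lost before any post-baseline FAF has had an event that Section 6.1 lists as intercurrent and handles by treatment policy, yet that subject leaves the population.

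Early loss could plausibly differ by arm. Sham involves no needle entry (Protocol 7.4). Phase 2 saw new exudation in 25/165 treated subjects against 1/81 on sham (Protocol 4.1.4), and intraocular inflammation has been reported (Protocol 4.2). The monthly arm has two scheduled injections, on Day 1 and at Month 1, before the Month 2 image.

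The copy-reference and tipping-point analyses exist to test this kind of loss. If its earliest cases are removed first, those analyses cannot speak to them. NL-BCVA raises a separate issue: it is a formally tested key secondary endpoint, and the absence of an FAF image is no reason to discard a valid acuity score.

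**Working it through.** **1. The main FAF model.** The response is change from baseline in FAF area at post-baseline visits. A subject with no post-baseline FAF has no response row, whether the set is called ITT or mITT. The only extra subjects the mITT rule removes from this model are undosed subjects who do have baseline and post-baseline FAF. The Section 15 rationale is sound here.

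**2. The imputation analyses.** The sample code in SAP Appendix 1.2.2 holds baseline as its own column and models Month 2 from it, so a subject with only a baseline FAF can be imputed. Section 6.2.3.1 illustrates a Month 12 shift of 0.48 mm² as 0.08 mm² at each of six visits from Month 2 (6 x 0.08 = 0.48). To receive the full shift, a subject must be missing from Month 2 onward, which normally means having no post-baseline FAF and so being outside mITT. The exception is an unscheduled or early-termination image that falls before the Month 2 window. Otherwise the largest total shift an mITT subject can receive is 5 x 0.08 = 0.40 mm². The scheme therefore presumes subjects whom the set excludes. Section 6.3.3 repeats these methods for the key secondary endpoints at Month 24.

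**3. The visit schedule (SAP Tables 8 and 10).**

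| Assessment | First scheduled post-baseline visit |
|---|---|
| NL-BCVA | Month 1 |
| FAF | Month 2 (also at early termination) |
| Reading speed, FRI | Month 6 |

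NL-BCVA can exist without FAF. Reading speed and FRI come after scheduled FAF at Months 2 and 4 and alongside FAF at Month 6.

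**4. The plan's own power figures.** Inputs from Protocol 12.5 and SAP 3.4: means 1.47, 1.70 and 2.13 mm²/year, SD 1.50, 200 per group, two-sided alpha 0.0495.

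- Standard error of a difference: 1.5 x sqrt(2/200) = 0.15 mm².
- Differences from sham: 2.13 - 1.47 = 0.66 (PM) and 2.13 - 1.70 = 0.43 (PEOM).
- Noncentrality: 0.66/0.15 = 4.40 and 0.43/0.15 = 2.87, on 597 degrees of freedom.
- Power: 99.24% and 81.53%; overall F test 98.44%. The plan gives 99.2%, 81.5% and 98.4%, so it reproduces.

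These figures use all 600 enrolled subjects, with no allowance for exclusions.

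**5. Size of the effect.** The documents do not give the number excluded. Assume 1-5% of an active arm is excluded and would have grown like sham. The arm mean then moves by the fraction times the difference.

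- PM: 0.01 x 0.66 = 0.007 to 0.05 x 0.66 = 0.033 mm².
- PEOM: 0.01 x 0.43 = 0.004 to 0.05 x 0.43 = 0.022 mm².
- Largest shift against the standard error: 0.033/0.15 = 0.22.

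**6. Power for PEOM across a range** (SD 1.5, the SAP's Month 12 alpha of 0.0496, equal exclusion in each arm assumed):

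| Excluded | n per group | Power, smaller n, full effect | Difference if kept and sham-like | Power, n = 200 |
|---|---|---|---|---|
| 0% | 200 | 81.6% | 0.4300 | 81.6% |
| 1% | 198 | 81.2% | 0.4257 | 80.8% |
| 2% | 196 | 80.8% | 0.4214 | 80.0% |
| 5% | 190 | 79.6% | 0.4085 | 77.5% |
| 10% | 180 | 77.4% | 0.3870 | 73.0% |

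PM power stays at or above 97.7% throughout. For subjects without post-baseline FAF, the loss in the third column would also occur in an MMRM labelled ITT.

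**The case against.** The strongest reply is that few subjects are at stake. FAF is in the early-termination column, Protocol 8.1.5 requires that visit of everyone who ends the study early, missed images are to be taken at the next visit, and subjects who stop treatment may stay in the study. An adverse event that stops treatment therefore excludes nobody by itself; exclusion on this ground needs no usable FAF at any later visit. That stands, and it limits the number. It does not bring it to zero. The synopsis and Protocol 11.8 only encourage or offer the early-termination visit, and the schedule places it at least 30 days after the last dosing visit unless the subject decides to stop at a scheduled visit before dosing.

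It can also be said that a lone Month 1 acuity score tells little about Month 24, and that adding reading speed and FRI to an endpoint-specific set would recover hardly anyone. Both are fair. Finally, the SAP discloses the change, summarises reasons for mITT exclusion and tabulates baseline for both sets, so an imbalance in exclusions would be visible. Seeing an imbalance is not the same as testing its effect on the result, and no planned analysis does that.

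**Conclusion.** The point holds in a limited form. No planned efficacy analysis covers all randomised subjects, and the reason given for the switch fits the FAF MMRM only. It does not justify leaving the earliest losses out of the two imputation analyses, or discarding NL-BCVA for want of FAF. The wording in Sections 6 and 6.1 conflicts with the set definition in Section 4.3.

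The likely numerical effect is small: at most 0.033 mm² under the 1-5% assumption. That figure takes every excluded active subject to grow like sham, whereas the SAP's copy-reference rule does so only for reasons potentially related to drug or lack of efficacy.

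A reader might infer three stronger things that the documents do not support:

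- **The analysis misses its stated estimand.** The population attribute in Section 6.1 and Table 2 is explicitly mITT. The mismatch is with the ITT wording of the research question and with the treatment-policy handling of early withdrawal.
- **The primary result is materially altered by the switch.** The MMRM loses subjects without post-baseline FAF under either label.
- **The missing-not-at-random shifts are understated by the same 1-5%.** The understatement depends on how many subjects with monotone missing data remain in mITT, which is not stated.

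**What to change.** - Run both Section 6.2.3.1 imputation analyses on all randomised subjects with a baseline FAF, imputing those with no post-baseline FAF.
- Analyse NL-BCVA in all randomised subjects with data on that endpoint. Apply the same rule formally to the other non-FAF endpoints, where it will change little.
- Keep mITT for the main FAF MMRM, or as a sensitivity set as in the protocol.
- Reconcile the all-randomised statement in Section 6 and the ITT wording in Section 6.1 with Section 4.3, and name the injection condition in Section 15.

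The cost is SAP wording and slightly more programming; the header of the sample code already anticipates an ITT run. Undosed subjects need a stated rule. Study day (13.3) counts from first dose, and the baseline fallback for undosed subjects appears only in Section 5.2, so the baseline and day anchor used for efficacy must be written down.

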### 12.7.2. Secondary Efficacy Analysis

The key secondary and secondary endpoints will be analyzed in the same fashion as the primary endpoint using mixed effect model. The binary secondary endpoints will be analyzed using Cochran-Mantel-Haenszel test stratified by the randomization stratification factors. Hypothesis testing for 3 key secondary endpoints will be performed in the order specified. The SAP will provide more details on multiplicity adjustment and the approach for alpha spending among the endpoints.

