#### *Secondary Efficacy Endpoints*

- Change from baseline in LL-BCVA at Month 12 and Month 24 as assessed by ETDRS chart.
- Change from baseline in low luminance deficit at Month 12 and Month 24.
- Change from baseline at each planned assessment in the total area of GA lesion(s) in the study eye (in mm^2) as assessed by FAF.
- Change from baseline in monocular critical print size (study eye), as assessed by MNREAD or Radner Reading Charts, at Month 12 and Month 24 (in select countries).
- Change from baseline in the NEI VFQ-25 distance activity subscale score at Month 12 and Month 24 (in select countries).

- Systemic Plasma concentration of pegcetacoplan over time (select sites).

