2.1.3. Secondary Objectives

To evaluate the efficacy of pegcetacoplan compared to sham in subjects with GA secondary to AMD with respect to:

- Low luminance best corrected visual acuity (LL-BCVA) score in the study eye
- Low luminance deficit (LLD) in the study eye
- Total area of GA lesion(s) in the study eye
- Monocular critical print size (study eye), as assessed by MNRead or Radner Reading Charts (in select countries)
- National Eye Institute Visual Functioning Questionnaire 25 Item Version (NEI VFQ-25) distance activity subscale score (in select countries)

To evaluate the pharmacokinetics (PK) of pegcetacoplan as assessed by systemic serum concentration of pegcetacoplan (in select sites).

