2.1.5. Exploratory Objectives

- To evaluate the efficacy of pegcetacoplan compared to sham in subjects with GA secondary to AMD as indicated by:
 - NEI VFQ-25 composite score
 - NEI VFQ-25 near activity subscale score (in select countries)
 - Comparison between study eye and fellow eye of change in GA lesion size
 - To evaluate the binocular reading speed as assessed by MNRead or Radner Reading Charts (in select countries)
 - To evaluate the binocular critical print size as assessed by MNRead or Radner Reading Charts (in select countries)
 - To evaluate the relationship between genetic polymorphisms associated with AMD with GA progression and response to pegcetacoplan
- To evaluate the incidence of new onset of subclinical CNV in the study eye.
- To assess sensitivity and specificity of a digital reading speed application to detect disease progression / regression (optional, select sites)
- To assess sensitivity and specificity of a digital visual function application to detect disease progression / regression (optional, select sites)

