6.4.1. Low Luminance Best-Corrected Visual Acuity (LL-BCVA)

LL-BCVA of the study eye will be summarized and analyzed in the similar fashion as the primary efficacy endpoint using MMRM described in Section 6.2.2. The model will include treatment (PM, PEOM, Sham), presence of CNV in the fellow eye (yes or no), and baseline GA lesion area ($< 7.5 \text{ mm}^2$ or $\geq 7.5 \text{ mm}^2$) as fixed effects; baseline LL-BCVA score as a covariate, time (in months) as a factor; the time \times treatment interaction term as well as the baseline LL-BCVA score \times time interaction term. Note, for the second year, only timepoints that were measured for all three treatment groups will be included in the model.

The observed values for the LL-BCVA will be summarized by treatment group and visit for both the study and the fellow eye. Summaries will present the descriptive statistics for baseline, absolute values and change from baseline data.

The mean change from baseline in the LL-BCVA score in the study eye \pm the standard error as well as the LS mean of the change from baseline in the LL-BCVA score in the study eye \pm the standard error will be plotted over time by treatment group.

The categorical changes (improvements of ≥ 15 , ≥ 10 to < 15 , ≥ 5 to < 10 , and minimal/no change (-4 to 4), worsening of ≥ 5 to < 10 , and ≥ 10 to < 15 and ≥ 15) for the study eye will be summarized by treatment group and visit.

Additionally, the average LL-BCVA score over the last 3 months for each reporting period (Month 10 - Month 12 for the Month 12 reporting; Month 22 - Month 24 for the Month 24 reporting) will be calculated for each subject who has at least one LL-BCVA assessment in these windows. The observed values for the LL-BCVA and changes from baseline will be summarized by treatment group for the study eye. Summaries will present the descriptive statistics for baseline, absolute values and change from baseline data.

The same subgroup analyses as described for NL-BCVA in Section 6.3.5 will also be repeated for LL-BCVA for the full 24 months.

All LL-BCVA data will be listed for the ITT set. In addition, the low luminance deficit will be calculated as the difference between NL-BCVA and LL-BCVA and listed for the ITT set.

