6.6.4. Digital Reading Index and Visual Function Application

The digital reading index will only be analyzed at the Month 24 reporting while the digital visual functional application will be analyzed at both the Month 12 and Month 24 reporting.

Descriptive summary statistics for baseline, absolute values, and change from baseline data to Month 12 and Month 24 will be provided by treatment group for digital reading index.

Additionally, the average digital reading index score over the last 3 months for each reporting period (Month 10 - Month 12 for the Month 12 reporting; Month 22 - Month 24 for the Month 24 reporting) will be calculated for each subject who has at least one digital reading index assessment in these windows. The observed values for the digital reading index and changes from baseline will be summarized by treatment group. Summaries will present the descriptive statistics for baseline, absolute values and change from baseline data.

Descriptive summary statistics for baseline, absolute values and change from baseline data to Month 12 and Month 24 will be provided by treatment group for digital visual function.

Additionally, the average digital visual function score over the last 3 months for each reporting period (Month 10 - Month 12 for the Month 12 reporting; Month 22 - Month 24 for the Month 24 reporting) will be calculated for each subject who has at least one digital visual function assessment in these windows. The observed values for the digital visual function and changes from baseline will be summarized by treatment group. Summaries will present the descriptive statistics for baseline, absolute values and change from baseline data.

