13.5.6. Low Luminance Deficit

$\text{LLD} = \text{NL-BCVA} - \text{LL-BCVA}$

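### Change in low luminance deficit is a protocol secondary endpoint and still a SAP objective, but the SAP only lists it, gives no reason, and plans no output that yields a confidence interval for it

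*SAP*

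**What the plan says.** **Low luminance deficit.** Protocol 12.7.2 lists "Change from baseline in low luminance deficit at Month 12 and Month 24" among the secondary efficacy endpoints. For the analysis it says: "The key secondary and secondary endpoints will be analyzed in the same fashion as the primary endpoint using mixed effect model". SAP 2.1.3 retains "Low luminance deficit (LLD) in the study eye" as a secondary objective. SAP 2.2.3 omits LLD from the secondary endpoints, while SAP 13.5.6 still defines it as normal luminance acuity (NL-BCVA) minus low luminance acuity (LL-BCVA). SAP 6.4.1, which gives LL-BCVA a full model, says only that "the low luminance deficit will be calculated as the difference between NL-BCVA and LL-BCVA and listed for the ITT set". SAP 15 confirms this: "No pre-specified analysis will be performed on the secondary endpoint of change from baseline in LLD over time. This data will only be listed".

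Baseline LLD is treated differently. It is summarised (SAP 5.2) and used to define subgroups for other endpoints (SAP 6.2.5).

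**Digital applications.** SAP 2.1.5 keeps the objective "To assess sensitivity and specificity of a digital reading speed application to detect disease progression / regression", and a matching one for the visual function application. SAP 2.2.4 defines the endpoints as change from baseline in each score. In SAP 6.6.4, descriptive statistics "will be provided by treatment group for digital reading index", and the same is planned for visual function, plus averages over the last three months of each reporting period.

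**The concern.** A stated objective should lead to an endpoint, and the endpoint to an analysis that can answer it. For LLD the chain breaks inside the SAP itself: there is an objective and a derivation, but no entry in the endpoint list and no post-baseline summary, treatment difference or interval. The statement in SAP 1 that the SAP supersedes the protocol's analysis plan does not mend this, because the unanswered objective stands in the SAP.

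If the plan is followed, the study report will state an objective on LLD and give subject-level values with no estimate of the effect of either pegcetacoplan regimen. An LLD analysis run later, on request, would not be pre-specified.

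The digital applications show the same break at exploratory level: the objectives concern diagnostic accuracy, and the planned outputs are summaries of the scores by arm.

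**Working it through.** The plan gives no figure for this point, so there is none to reproduce. The check has three steps.

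**1. Tracing LLD through the documents**

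- Protocol objective (5.1.3): present.
- Protocol endpoint (12.7.2): present, Months 12 and 24. That section lists five secondary efficacy endpoints (LL-BCVA, LLD, GA area, critical print size, NEI VFQ-25 distance activity) and one pharmacokinetic endpoint. LLD is one of the five.
- Protocol analysis (12.7.2): mixed model.
- SAP objective (2.1.3): present.
- SAP endpoint (2.2.3): absent, although Section 15 still calls LLD a secondary endpoint.
- SAP analysis (6.4.1, 15): listing only.
- Reason (15): none. The same section does give reasons for the change of analysis set and for the pharmacokinetic parameters.

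Lack of data is not an evident reason. NL-BCVA and LL-BCVA are both scheduled on Day 1 and at Months 12 and 24 in every arm (Protocol Appendices A to D). Both also stay marked as required at those visits in the COVID-19 minimum schedules (Appendix K).

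**2. Can the two acuity models stand in for an LLD model?**

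Write d(NL) and d(LL) for the treatment differences from SAP 6.3.2.3 and 6.4.1.

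- Point estimate: d(LLD) ≈ d(NL) − d(LL). This is only approximate. The models adjust for different baseline scores and may rest on different visits, since the COVID-19 minimum schedules keep LL-BCVA at fewer visits than NL-BCVA.
- Variance: Var(d(LLD)) = Var(d(NL)) + Var(d(LL)) − 2 Cov(d(NL), d(LL)). The two models are fitted separately, so the covariance is not an output.

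To see how much the missing term matters, assume that both differences have the same standard error s and correlation ρ. The documents give neither, so ρ is shown over a range. Then SE(d(LLD)) = s√(2(1 − ρ)):

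- ρ = 0.3: s√1.4 = 1.18s
- ρ = 0.5: s√1.0 = 1.00s
- ρ = 0.8: s√0.4 = 0.63s

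Over this range the standard error changes by a factor of 1.18/0.63, about 1.9. A reader willing to assume ρ ≥ 0 could use s√2 = 1.41s as an upper bound, but that gives a conservative bound and not the interval.

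**3. Digital applications**

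Sensitivity and specificity need a reference standard for progression or regression, a cut-off for a positive application result, and a cross-classification of the two. SAP 6.6.4 has none of these. SAP 10 plans no other analyses. No separate report is mentioned, whereas SAP 6.6.5 does mention one for the genetic data. Section 15 records several added exploratory endpoints but not this replacement. Neither measure can be obtained from the planned tables.

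**The case against.** The case for leaving the plan alone is as follows. The LLD change is stated openly in Section 15 and matches the endpoint list in SAP 2.2.3. LLD is an exact function of two variables that each receive a full model, descriptive summaries and categorical changes. Non-key secondary endpoints carry no hypothesis test (SAP 6.5). Subject-level LLD is listed for the whole ITT set, so anyone with the data could compute the interval. What is lost is one interval on a derived contrast, and deleting the objective would cure the inconsistency just as well.

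Most of this stands as a limit on importance. It does not supply a reason for the change, and a listing does not answer an objective. Deleting the objective would make the SAP consistent, but it would give up a protocol endpoint when the data to estimate it are being collected anyway.

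Two stronger readings are tempting:

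- *Selective reporting.* A reader might infer that an unfavourable endpoint was dropped. The documents do not support this. The change is disclosed, the values are listed, and Protocol 12.3 requires the SAP to be final before database lock.
- *An endpoint discarded despite both components being available at every visit.* The schedules say otherwise. LL-BCVA is not done at screening. The every-other-month groups have no odd-month visits in year 2. In the COVID-19 minimum schedules LL-BCVA remains required after baseline only at Months 6, 12, 18 and 24. What matters here is narrower: both components are scheduled at baseline, Month 12 and Month 24.

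On the applications, it is fair to say that they are optional, run at select sites and are exploratory, and that Protocol 12.7.3 promises only summary statistics. But the quantities it lists for summary are sensitivity and specificity, so the mismatch remains. Which reference standard would suit is a clinical choice that the documents do not settle, and this review should not prescribe one.

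**Conclusion.** The LLD point holds. One of five protocol secondary efficacy endpoints, still a SAP objective, has no planned estimate, and none of the planned outputs yields a confidence interval for it. The change is disclosed but unexplained. The conclusion rests on tracing the sections and on the variance identity; the correlations of 0.3 to 0.8 are illustrative assumptions and do not carry it. No precision in letters is claimed for an LLD analysis, because the documents give no standard deviation for LLD change.

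The consequence is limited. The primary and key secondary analyses and the type I error are untouched. The change is worth making because it costs little and lets the trial answer a question that it still poses.

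The digital-application mismatch is real but secondary: two exploratory objectives that the planned analyses cannot answer, and a change not recorded in Section 15.

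**What to change.** **LLD.** In SAP 6.4.1, add a repeated-measures model of change from baseline in study-eye LLD in the LL-BCVA form: treatment, fellow-eye CNV, baseline GA area category, time, time × treatment, baseline LLD and baseline LLD × time. In year 2, use only timepoints common to all arms. Report LS mean differences for each pegcetacoplan arm against sham with 95% confidence intervals at Months 12 and 24, with no alpha assigned. Restore LLD to SAP 2.2.3 and delete the Section 15 item. The cost is SAP wording and one more descriptive table; the data are already collected. If the sponsor prefers not to analyse LLD, the minimum is to remove the objective from SAP 2.1.3 and give the reason in Section 15.

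**Digital applications.** Choose one of two routes. The first is to pre-specify the sponsor's own reference standard for progression or regression and its own cut-off for each application, and report sensitivity and specificity with 95% confidence intervals. The second is to reword the SAP 2.1.5 objectives to match the descriptive analysis and record the change in Section 15. The first needs clinical input and one table, and its precision depends on how many optional-site subjects have both measures. The second is wording only.
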